### **Rescue Medication Days per Month in the OLE Phase**

Analyses are based on evaluable OL rimegepant mITT subjects with eDiary reference time point dates in the on-OL rimegepant efficacy analysis period.

The number of rescue medication days per month in the OLE phase will be prorated to 28 days and derived as follows:

- Month (i.e., 4-week interval) in the on-OL rimegepant efficacy analysis period:  $28 \times (\text{total number of rescue medication days in the month}) / (\text{total number of efficacy data days in the month})$ . Subjects must have  $\geq 14$  days of efficacy data (not necessarily consecutive) in the specified month to be evaluable.
- Overall OL rimegepant mean:  $28 \times (\text{total number of rescue medication days through Month 13 in the on-OL rimegepant efficacy analysis period}) / (\text{total number of efficacy data days through Month 13 in the on-OL rimegepant efficacy analysis period})$ .

The number of rescue medication days per month in the OLE phase will be summarized descriptively as a continuous parameter (including 2-sided normal 95% CIs for mean) by treatment group and overall in each month of the OLE phase and overall OLE mean.

### **6.3.2.3 MSQoL in the DBT Phase**

The MSQoL will be assessed at early termination and the following visits: baseline; Week 12 of the DBT phase; and Weeks 24 and 64 of the OLE phase.

The MSQoL consists of 14 items across the following 3 domains: (1) restrictive role function, (2) preventative role function and (3) emotional function. Refer to the BHV3000 Core SAP for calculating transformed domain scores and imputing missing data.

Measurements will be first selected from the on-DBT efficacy period, and then slotted into the Week 12 analysis visit window (see Week 12 of the analysis visit window for outcome research

[OR] endpoints column in Table 4). If a subject has multiple values in the analysis visit window, then the non-missing value closest to the target date for the visit will be used; in the case of a tie, the latest value collected will be used.

See Sections 6.2.5, 7.4, and 7.5 for definitions of baseline, analysis periods, and analysis visit windows, respectively.

### **Descriptive Analyses**

Values and changes from baseline in transformed scores for each domain will be summarized descriptively (included 2-sided normal 95% CIs for mean change) as continuous parameters by treatment group at baseline and Week 12.

As-randomized analyses will be based on evaluable mITT subjects with MSQoL domain scores at both baseline and Week 12 of the on-DBT efficacy analysis period. See Section 6.6.1 for as-treated analyses of MSQoL in the DBT and OLE phases for treated subjects.

### **Treatment Group Comparisons**

Analyses will be based on evaluable mITT subjects with MSQoL restrictive role function domain scores at both baseline and Week 12 of the on-DBT efficacy analysis period.

A generalized linear model will have the following variables: Week 12 change from baseline in the restrictive role function transformed score as the dependent variable; baseline restrictive role function transformed score as a covariate; treatment group and the prophylactic migraine medication use at randomization as fixed effects. The model will be repeated by prophylactic migraine medication use at randomization (yes, no). The following model estimates will be reported:

- LSM change from baseline at Week 12, SE, and 95% CI by randomization stratum (yes, no, overall) for each treatment group
- Difference in LSM changes from baseline between treatment groups (rimegepant – placebo) at Week 12, SE, 95% CI, and p-value by randomization stratum (yes, no)
- Difference in LSM changes from baseline between treatment groups (rimegepant – placebo) at Week 12, SE, 95% CI, and p-value. Results will support the fifth secondary objective.

#### **6.3.2.4 MIDAS in the DBT Phase**

The MIDAS is a retrospective, patient-administered, 5-item questionnaire that measures headache-related disability as lost time due to headache from paid work or school, household work, and non-work activities. The MIDAS will be assessed at early termination and the following visits: baseline; Week 12 of the DBT phase; and Weeks 24 and 64 of the OLE phase.

Refer to the BHV3000 Core SAP for calculating MIDAS scores (i.e., total, absenteeism, presenteeism, item) and imputing missing data.

Measurements will be first selected from the on-DBT efficacy period, and then slotted into the Week 12 analysis visit window; see Section 6.3.2.3.

## Descriptive Analyses

Values and changes from baseline in total, absenteeism, presenteeism, and item scores will be summarized as described in Section 6.3.2.3.

As-randomized analyses will be based on evaluable mITT subjects with MIDAS scores at both baseline and Week 12 of the on-DBT efficacy analysis period. See Section 6.6.2 for as-treated analyses of MIDAS in the DBT and OLE phases for treated subjects.

## Treatment Group Comparisons

Analyses will be based on evaluable mITT subjects with MIDAS total scores at both baseline and Week 12 of the on-DBT efficacy analysis period.

A generalized linear model will have the following variables: Week 12 change from baseline in the total score as the dependent variable; baseline total score as a covariate; treatment group and prophylactic migraine medication use at randomization as fixed effects. The model will be repeated by prophylactic migraine medication use at randomization (yes, no). The same model estimates as those described in Section 6.3.2.3 will be reported. Results will support the last secondary objective.

### 6.3.2.5 Overall Summary of Primary and Secondary Endpoints

An overall summary of treatment comparisons of all primary and secondary endpoints tested hierarchically will present the following statistics:

- Continuous endpoints involving change from OP or baseline
  - Overall LSM change and 95% CI for each treatment group
  - Difference in overall LSM changes between treatment groups (rimegepant – placebo), 95% CI, and p-value.

This applies to the following endpoints: primary endpoint; secondary endpoint of change in mean number of migraine days per month in the overall DBT phase; secondary endpoint of change in mean number of migraine days per month in the first month of the DBT phase; MSQoL restrictive role domain score change from baseline at Week 12; and MIDAS total score change from baseline at Week 12.

- Continuous endpoints not involving change from OP or baseline
  - Overall LSM and 95% CI for each treatment group
  - Difference in overall LSMs between treatment groups (rimegepant – placebo), 95% CI, and p-value.

This applies to the secondary endpoint of the mean number of rescue medication days per month in the last month of the DBT phase.

- Binary endpoints
    - Overall response rate (“n/N”), stratified risk, and 95% CI for each treatment group
-

- Overall stratified risk difference between treatment groups (rimegepant – placebo), 95% CI, and p-value.

This applies to the secondary endpoint of percentage of subjects with  $\geq 50\%$  reduction in mean number of moderate or severe migraine days per month in the last month of the DBT phase.

Analyses will be based on principal methods described in Sections 6.3.1.1 and 6.3.2. Endpoints will be displayed in the order presented in Sections 1.2.1 and 1.2.2. P-values that are determined to be significant based on the testing hierarchy will be flagged.

### **6.3.3 Exploratory Efficacy Endpoints**

#### **6.3.3.1 Reduction in MRM Days per Month**

Female subjects will record their menstrual period start and stop dates in a menstrual period log. Menstruating females will be identified as females with either (1) a “yes” response to the question about experiencing menstrual periods on the Demographics CRF (see Section 6.2.5), or (2) at least one complete menstrual period start date from the Menstrual Period Log CRF.

An eDiary reference time point date is considered to be exclusively in a menstrual interval if the complete menstrual period start date – 2 days  $\leq$  eDiary reference time point date  $\leq$  complete menstrual period start date + 2 days.

A day of MR efficacy data is defined as a non-missing eDiary efficacy date inclusively in a menstrual interval.

An MRM day is defined as a non-missing eDiary migraine date inclusively in a menstrual interval.

MRM days per month will be assessed as “MRM days per 4 weeks” to correspond with the 4-week visit schedule. MRM days per month are based on data from the previous visit to the current visit (i.e., 4-week interval), and are prorated to account for missing migraine reports.

A by-subject listing of menstrual periods that includes efficacy analysis period will be provided for enrolled female subjects, and will display COVID-19 visit impact code for visits impacted by COVID-19 (see Section 9.1.5.2).

A by-subject listing of MRM days will be provided for menstruating female treated subjects, and will present the following: number of MRM days per month by migraine severity (total; moderate or severe) in the OP efficacy analysis period, overall DBT mean, overall OL rimegepant mean, and in each month of the on-DBT and on-OL rimegepant efficacy analysis periods, number of days of MR efficacy data in these aforementioned periods, overall DBT mean, and overall OL rimegepant mean; MRM day values, changes and percent changes from OP in the aforementioned months, overall DBT mean, and overall OL rimegepant mean.

#### **Reduction in MRM Days per Month in the DBT Phase**

The number of MRM days per month in the DBT phase will be examined relative to the number of MRM days per month in the OP for menstrual migraine evaluable mITT menstruating female subjects, i.e., mITT menstruating females with  $\geq 1$  day of eDiary MR efficacy data and  $\geq 14$  days of eDiary efficacy data (not necessarily consecutive) in both the OP analysis period and at least one month (i.e., 4-week interval) in the on-DBT efficacy analysis period (see Section 7.6.2).

Months in the DBT phase are defined in Section 6.3.1.2.

Analyses will be based on eDiary efficacy dates in the OP analysis period and on-DBT efficacy analysis period.

The number of MRM days per month will be prorated to 28 days, and derived as follows:

- OP:  $28 \times (\text{total number of MRM days in the OP analysis period}) / (\text{total number of efficacy data days in the OP analysis period})$ .
- Month (i.e., 4-week interval) in the on-DBT efficacy analysis period:  $28 \times (\text{total number of MRM days in the month}) / (\text{total number of efficacy data days in the month})$ . Subjects must have at least one day of MR efficacy data in the specified month to be evaluable.
- Overall DBT mean:  $28 \times (\text{total number of MRM days through Month 3 in the on-DBT efficacy analysis period}) / (\text{total number of efficacy data days through Month 3 in the on-DBT efficacy analysis period})$ .

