#### **6.3.1.1 Reduction in Migraine Days per Month in the DBT Phase: Primary Efficacy Endpoint**

The number of migraine days per month in the DBT phase will be examined relative to the number of migraine days per month in the OP for evaluable mITT subjects, i.e., subjects with  $\geq$

14 days of eDiary efficacy data (not necessarily consecutive) in both the OP analysis period and  $\geq 1$  month (i.e., 4-week interval) in the on-DBT analysis period.

Months in the DBT phase are defined as follows:

- Month 1 ( $\leq 4$  weeks; study days 1 to 28)
- Month 2 ( $> 4$  to  $\leq 8$  weeks; study days 29 to 56)
- Month 3 ( $> 8$  to  $\leq 12$  weeks; study days 57 to 84)

Analyses will be based on eDiary efficacy dates in the OP and on-DBT efficacy analysis periods.

The number of migraine days per month will be prorated to 28 days and derived as follows:

- OP:  $28 \times (\text{total number of migraine days in the OP analysis period}) / (\text{total number of efficacy data days in the OP analysis period})$ .
- Month (i.e., 4-week interval) in the on-DBT efficacy analysis period:  $28 \times (\text{total number of migraine days in the month}) / (\text{total number of efficacy data days in the month})$ . Subjects must have  $\geq 14$  days of efficacy data (not necessarily consecutive) in the specified month to be evaluable.
- Overall DBT mean:  $28 \times (\text{total number of migraine days through Month 3 in the on-DBT efficacy analysis period}) / (\text{total number of efficacy data days through Month 3 in the on-DBT efficacy analysis period})$ .

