## Treatment Group Comparisons

A generalized linear mixed effect model similar to the one described for the primary endpoint in Section 6.3.1.1 will be used with the following variables: change from the OP in number of total MRM days per month as the dependent variable; subject as a random effect; number of total MRM days per month in the OP as a covariate; treatment group, prophylactic migraine medication use at randomization, month (i.e., months 1 to 3 of the DBT phase), and the month-by-treatment group interaction as fixed effects. The model will be repeated by prophylactic migraine medication use at randomization (yes, no). The same model estimates will be reported as for the primary endpoint (see Section 6.3.1.1).

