### Reduction in MRM Days per Month in the OLE Phase

The number of MRM days per month in the OLE phase will be examined relative to the number of MRM days per month in the OP for menstrual migraine evaluable OL rimegepant mITT menstruating female subjects, i.e., defined as OL rimegepant mITT menstruating female subjects with  $\geq 1$  day of MR efficacy data and  $\geq 14$  days of eDiary efficacy data (not necessarily consecutive) in both the OP analysis period and at least one month (i.e., 4-week interval) in the on-OL rimegepant efficacy analysis period.

Months in the OLE phase are defined in Section 6.3.1.2.

Analyses will be based on eDiary efficacy dates in the OP and on-OL rimegepant efficacy analysis periods.

The number of MRM days per month will be prorated to 28 days and derived as follows:

- OP: See Section 6.3.1.1.
- Month (i.e., 4-week interval) in the on-OL rimegepant efficacy analysis period:  $28 \times (\text{total number of MRM days in the month}) / (\text{total number of efficacy data days in the month})$ .  
Subjects must have  $\geq 1$  day of MR efficacy data in the specified month to be evaluable.
- Overall OL rimegepant mean:  $28 \times (\text{total number of MRM days through Month 13 in the on-OL rimegepant efficacy analysis period}) / (\text{total number of efficacy data days through Month 13 in the on-OL rimegepant efficacy analysis period})$ .

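### In the exploratory menstrually-related migraine (MRM) analysis, a month counts with one menstrual diary day and no 14-day minimum, yet is prorated to 28 days, so a short month can exceed the possible count

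*SAP*

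**What the plan says.** SAP 6.3.3.1 counts an MRM day as follows: "An MRM day is defined as a non-missing eDiary migraine date inclusively in a menstrual interval". The interval runs from 2 days before to 2 days after a recorded period start.

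For the double-blind (DBT) phase it states: "The number of MRM days per month will be prorated to 28 days, and derived as follows". The monthly value is 28 times MRM days, divided by all efficacy data days in that month. The condition on the month is: "Subjects must have at least one day of MR efficacy data in the specified month to be evaluable". The open-label extension (OLE) text has the same rule, at least 1 "day of MR efficacy data in the specified month to be evaluable".

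A 14-day requirement appears only at cohort level: at least 14 "days of eDiary efficacy data (not necessarily consecutive) in both the OP analysis period and at least one month".

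The primary endpoint (SAP 6.3.1.1) differs. Each month needs at least 14 "days of efficacy data (not necessarily consecutive) in the specified month to be evaluable". Rescue medication days (6.3.2.2) and triptan or ergotamine days (6.3.3.3) carry the same month-level floor. Protocol Appendix 3 defines monthly eDiary data as needing at least 14 diary days in the interval before proration.

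The SAP revision history for version 10.0 says the MRM cohorts were redefined to bring these analyses into line with those of migraine days. SAP section 8 reports no departures from the protocol's planned analyses.

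The monthly MRM values feed a mixed model with "change from the OP in number of total MRM days per month as the dependent variable", reported with treatment differences, confidence intervals and p-values.

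**The concern.** Version 10.0 aligned the cohort but not the month rule. A woman who qualifies through a well-recorded Month 1 can contribute a Month 2 or 3 with only a few diary days, provided one lies in a menstrual window. Such months can arise by design: SAP 7.4 ends the on-DBT efficacy period one day after the last dose, so stopping early in a month leaves a truncated one.

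Proration assumes that the recorded days represent the month. That is doubtful for an event confined to a 5-day window: a few days in or near the window are scaled up as if the window lasted all month. The result can be a count that no month could contain. The large values enter only after baseline, so they push change scores upward. If truncated months are more common in one arm, the distortion need not cancel.

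**Working it through.** **The plan's own figure.** The documents give no numerical figure for the MRM endpoint. The only design figure is power for the primary endpoint: 370 per arm, 1-day difference, SD 3.75, roughly 95%. It reproduces: SE = 3.75 × √(2/370) = 0.276; 1/0.276 − 1.96 = 1.67; power 95.2%. It has no bearing on this point.

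**Inputs.** Window: −2 to +2 days around period start = 5 days (SAP 6.3.3.1, using the inequalities as printed). Monthly value: 28 × m/e, with m = MRM days and e = efficacy data days in the month. With one period m ≤ min(e, 5); with two, m ≤ min(e, 10).

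**Possible true counts.** At most 5 in a month with one period and 10 with two. Two full windows fit into 28 days only if the cycle is about 23 days or shorter (an assumption; cycle length is not in the documents). A true count of 28 would need 28/5 = 5.6 periods.

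**Values the rule permits.**

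| Diary days e | One MRM day (28/e) | Maximum, one period | Maximum, two periods |
|---|---|---|---|
| 1 | 28.0 | 28.0 | 28.0 |
| 3 | 9.3 | 28.0 | 28.0 |
| 5 | 5.6 | 28.0 | 28.0 |
| 7 | 4.0 | 20.0 | 28.0 |
| 10 | 2.8 | 14.0 | 28.0 |
| 13 | 2.2 | 10.8 | 21.5 |
| 14 | 2.0 | 10.0 | 20.0 |
| 28 | 1.0 | 5.0 | 10.0 |

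The rows below 14 days are what a month-level floor would remove. At the floor the maxima are 28 × 5/14 = 10.0 and 28 × 10/14 = 20.0.

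**Baseline.** The OP needs 14 days for the cohort, so its one-period maximum is 10.0. Eligibility requires 24 completed diary reports (protocol 5.3), which gives 28 × 5/24 = 5.8.

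**Overall DBT mean.** This descriptive value divides all MRM days by all diary days through Month 3. Every cohort member has at least 14 days in that denominator, so a short month carries only its own few days' weight.

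**Effect on an arm mean.** The number of menstruating women per arm is not given; assume 50 to 300. One month recorded as 28 instead of 5 moves a raw arm mean by 23/50 = 0.46 to 23/300 = 0.08 day. One recorded as 9.3 instead of 5 moves it by 4.3/50 = 0.09 to 4.3/300 = 0.01 day.

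**The case against.** The case against concerns strength, not the reading of the rule, and much of it stands.

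- A reader might infer that the analysis will yield months of 28. The documents show only that the rule permits it. With one period it needs at most 5 diary days, all in the window and all migraine days. Assuming a 28-day cycle, a run of 2, 3, 4 or 5 consecutive days lies wholly in the window at 4, 3, 2 or 1 of 28 starting positions, before asking whether each is a migraine day. Milder inflation, such as 9.3, needs less coincidence.
- A reader might infer that short months dominate the comparison. Nothing supports that: the frequency of short months and any difference in stopping between arms are not in the documents.
- A reader might infer that no 14-day rule applies. One does, to the OP and to at least one month per woman.
- The endpoint is exploratory, outside the testing hierarchy, with descriptive p-values (SAP 6.1.2). OLE results are descriptive only, so no modelled comparison is at stake there.
- A 14-day floor is not a full cure. It still permits 10.0 or 20.0, twice the possible counts, because a window-limited count is still scaled by all diary days.

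None of this explains why MRM months follow a looser rule than the other prorated monthly endpoints. The SAP gives no reason.

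**Conclusion.** The point holds as an inconsistency in an exploratory analysis. The month-level MRM rule departs from the study's 14-day standard, from Protocol Appendix 3 and from the stated purpose of version 10.0. It can give values above the possible 5 (one period) or 10 (two), up to a bound of 28.

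Exposed are the by-month DBT means, the mixed-model differences and the OLE monthly descriptive means. The OP value, the descriptive overall DBT mean, the primary and secondary endpoints and type I error control are not materially affected. The table of permitted values rests only on the SAP's formula and window. The arm-mean shifts rest on an assumed 50 to 300 women per arm and show scale only. How often short months occur cannot be derived from the documents.

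**What to change.** In SAP 6.3.3.1, for both phases, make a month evaluable only with at least 14 efficacy data days and at least 1 MR efficacy day in that month. Carry the same condition into the missing-data tables there, which now count MR days alone. Also correct the DBT cross-reference for months: it points to 6.3.1.2, which defines OLE months, instead of 6.3.1.1.

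This restores the study's own standard and lowers the maximum from 28 to 10.0 or 20.0. Scaling by MR diary days within the window would be needed to remove the remaining over-scaling; that is a larger change and need not hold up this one.

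The text edit is one phrase in two places, but there are further costs. A few short months become missing, in the descriptive summaries as well as in the model. Version 10.0 was written after the final database lock, so the change should be labelled post hoc. Report the number of MRM months with fewer than 14 diary days by arm, and rerun the MRM tables and model so that readers can see whether the rule made a difference.

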### Missing MR Efficacy Data

Missing MR efficacy data in the OP and DBT phases will be assessed using the number and percentage of mITT menstruating female subjects in the following categories:

- Evaluable
- Not evaluable, i.e., no days of MR efficacy data in the OP and no days of MR efficacy data in all 3 months (i.e., all 3 4-week intervals) of the DBT phase
  - No days of MR efficacy data in the OP
  - No days of MR efficacy data in any of the following months (i.e., 4-week intervals) of the DBT phase:
    - Month 1:  $\leq 4$  weeks
    - Month 2:  $> 4$  to  $\leq 8$  weeks
    - Month 3:  $> 8$  to  $\leq 12$  weeks

### Descriptive Analyses

Values and changes (both absolute and percent) from the OP in the number of MRM days per month in the DBT phase will be summarized descriptively as continuous parameters (including 2-sided normal 95% CIs for mean change) by treatment group and migraine severity (total; moderate or severe) in each month of the DBT phase and overall DBT mean.

---

Analyses are based on evaluable mITT menstruating female subjects. In the percent change analyses, subjects must also have  $\geq 1$  MRM day of appropriate migraine severity in the OP analysis period to be included.

## Treatment Group Comparisons

A generalized linear mixed effect model similar to the one described for the primary endpoint in Section 6.3.1.1 will be used with the following variables: change from the OP in number of total MRM days per month as the dependent variable; subject as a random effect; number of total MRM days per month in the OP as a covariate; treatment group, prophylactic migraine medication use at randomization, month (i.e., months 1 to 3 of the DBT phase), and the month-by-treatment group interaction as fixed effects. The model will be repeated by prophylactic migraine medication use at randomization (yes, no). The same model estimates will be reported as for the primary endpoint (see Section 6.3.1.1).

